4.4. Radiotherapy technique

4.4.1. Quality assurance for stereotactic radiotherapy

Participation requirements:

The following requirements are mandatory for all participating institutions and need to be achieved before the enrollment of patients at the respective site:

- Linear accelerator with ≥ 6 MV photons designed for stereotactic radiosurgery
- Patient immobilization: Individual patient immobilization with a dedicated thermoplastic mask system that is designed for stereotactic radiosurgery
- Image Guidance: A kV X-ray based imaging system using i) an on-board CT, ii) a supplementary in-room CT or iii) in-room X-ray is mandatory. An image-guidance system relying solely on surface tracking (e.g. Vision RT) is not acceptable.
- Collimation of irradiation: Multileaf collimator (MLC) with leaf width ≤ 5 mm centrally or cylindrical collimators of equivalent size (Schmitt et al. 2020).
- Mechanical accuracy: Spatial dose placement uncertainties need to be a maximum of 1 mm in system-specific end-to-end tests.
- Dosimetric accuracy: Point based plan-to-measurement differences must be $\leq 3\%$ within the target using system-specific end-to-end or delivery-quality-assurance tests with homogeneous phantoms
- Dose calculation grid size: The dose calculation grid size has to be 2 mm or finer according to ICRU 91 (ICRU 2017).
- Dose calculation algorithm: Advanced type-b model-based dose calculation algorithms like Monte Carlo techniques and deterministic solvers (e.g. Acuros AXB, Varian) must be used (ICRU 2017).
- Dedicated quality assurance measures: Small field dosimetry for commissioning, system-specific end-to-end tests, the regular check of mechanical accuracy according to system specific instructions and daily quality control of the compliance of the image guidance system with the treatment isocenter are mandatory.
- The planning CT slice thickness should be ≤ 1.5 mm.
- MRI for target volume delineation, which must be performed no longer than 14 days before the start of RT of brain metastases in this study (Seymour et al. 2015).

- The MRI study used for target volume delineation must contain a high-resolution, contrast-enhanced T1-weighted series, for example T1-MP-RAGE, with a maximum slice thickness of 1 mm and isotropic resolution (see 7.1 for details).
- Distortions in the MRI for target volume definition must be minimized: **Vendor-specific 3D distortion correction** for gradient non-linearity-related distortions **is mandatory** and distortions due to magnetic field inhomogeneity should be minimized by patient-specific active shimming and appropriate pixel bandwidths. (Putz et al. 2020)
- Treatment planning system: A treatment planning system capable of stereotactic radiosurgery planning that allows for highly accurate rigid co-registration of planning CT and MRI images.
- Stereotactic radiotherapy may be delivered using coplanar and non-coplanar stereotactic arcs. Multiple isocenters and intensity modulated radiotherapy may be used to enable conformal dose delivery.
- Existing local expertise in treating patients with SRS or FSRT for brain metastases is required, i.e. at least 100 cranial SRS or FSRT treatments have been performed in the previous 3 years.

4.4.2. Patient positioning

Dedicated thermoplastic mask fixation systems designed for stereotactic radiosurgery will be used to position the patients for stereotactic radiotherapy and CT-based treatment planning in order to minimize positioning inaccuracy.

Image guidance is mandatory. A kV X-ray based imaging system using i) an on-board CT, ii) a supplementary in-room CT or iii) stereoscopic X-ray is required for patient positioning and after each couch rotation. An image-guidance system relying solely on surface tracking (e.g. Vision RT) is not acceptable.

Overall, a targeting accuracy of 1 mm or better should be achieved (Kocher et al. 2014).

4.4.3. Target volume delineation

The gross tumor volume (GTV) is defined as the demonstrable extent of the metastasis, as determined by high-resolution, contrast-enhanced T1-weighted magnetic resonance imaging with a maximum layer thickness of 1.5 mm performed no more than 14 days before the start of RT. Accurate GTV segmentation must be performed in each available layer at the voxel level.

Planning target volume definition varies according to treatment arm.

- Control arm – Single-session SRS according to RTOG 9005:

PTV = GTV + up to 1 mm margin depending on institution-specific accuracy

- Experimental arm - Fractionated stereotactic radiotherapy:
PTV = GTV + 2 mm (i.e., the PTV corresponds to GTV with 2 mm isotropic expansion)

If isotropic expansion leads to overlapping with a critical organ at risk (OAR), such as the optic system, it is permissible to reduce the safety margin to 0 mm at the affected sites.

4.4.4. Definition of organs at risk (OAR)

Segmentation of the following organs at risk (OARs) must be performed during radiation planning: eyes (left & right), optic nerves (left & right), chiasma, pituitary gland, cochlea (left & right), and brain stem. Segmentation of the cervical spinal cord is also necessary in patients with very caudal lesions (cerebellum). In general, all OARs must be segmented completely along their entire extent (exception: spinal cord). The segmentation of optic nerves, chiasma, pituitary gland, cochlea and brainstem must be performed with the aid of the high-resolution MRI (layer thickness of the sequences used for segmentation must not exceed 1.5 mm).

4.4.5. Dose prescription and dose specification

Prescribing, recording and reporting should be performed according to the ICRU Report 91 guidelines. (ICRU 2017)

In the control arm, brain metastases will be treated by single-fraction SRS according to RTOG 9005 guidelines. These patients will receive a single fraction of either 24 Gy (diameter: ≥ 1 cm and < 2 cm), 18 Gy (diameter: ≥ 2 cm and < 3 cm) or 15 Gy (diameter: ≥ 3 cm and ≤ 4 cm), depending on the largest diameter of the metastasis to be irradiated.

Metastases in the experimental arm will be treated with hypofractionated stereotactic radiotherapy (FSRT). Patients in the FSRT group will receive a total dose of 48 Gy in 12 daily fractions of 4 Gy each (with weekend breaks).

The target-encompassing isodose should be 50-80% in the control arm (single-fraction SRS) and 80% in the experimental arm (FSRT).

The dose specification will be set to the target-encompassing isodose normalized to the maximum dose ($D_{max} = 100\%$). The dose calculation grid size has to be 2 mm or finer according to ICRU 91 (ICRU 2017). Advanced type-b model-based dose calculation algorithms like Monte Carlo techniques and deterministic solvers (e.g. Acuros AXB, Varian) must be used (ICRU 2017).

4.4.6. Radiotherapy plan quality requirements

The plan quality is assessed using the established metrics by Shaw et al. (Shaw et al. 1993) as well as by the new ICRU 91 guidelines (ICRU 2017).

The specified values have to be achieved.

Conformity Index:

The Conformity Index is defined as $CI = V_{RI}/TV$, where V_{RI} is the volume of the encompassing prescription isodose and TV is the volume of the planning target volume

Per Protocol: Conformity Index ≥ 1.0 and ≤ 2.0

Acceptable variation: Conformity Index ≥ 0.9 and < 1.0 OR > 2.0 and ≤ 2.5

Major deviation (Unacceptable): all other

Note: In the control arm (SRS), if normal brain tissue constraints can't be met otherwise, the lower boundary for per protocol is decreased to 0.9 and the lower boundary for acceptable variation is lowered to 0.8 (see below).

Coverage:

The Coverage is defined as $Q = I_{min}/I_{pre}$, where I_{min} is the minimum dose, the target receives and I_{pre} is the prescribed dose.

Per Protocol: Coverage ≥ 0.9

Acceptable variation: Coverage 0.8 – 0.9

Major deviation (Unacceptable): all other

Note: In the control arm (SRS), if normal brain tissue constraints can't be met otherwise, the lower boundary for per protocol is decreased to 0.8 and the lower boundary for acceptable variation is lowered to 0.7 (see below).

Homogeneity Index:

The Homogeneity Index is defined as $HI = I_{max}/I_{pre}$, where I_{max} is the maximum dose, the target receives and I_{pre} is the prescribed dose.

Per Protocol: Homogeneity Index ≤ 2

Acceptable variation: Homogeneity Index > 2.0 and ≤ 2.5

Major deviation (Unacceptable): all other

4.4.7. Simulation and documentation

Isodose distributions, dose-volume histograms (DVHs) for organs at risk and target volumes (GTV, PTV) are mandatory for radiation planning and must be documented. Image-guided radiotherapy (IGRT) with daily position

verification is also mandatory. All radiation treatment records must be kept on file for 30 years, pursuant to Article §85 (3) of the German Ordinance on the Protection against Damage and Injuries Caused by Ionizing Radiation (Radiation Protection Ordinance, StrlSchV). Prescribing, recording and reporting should be performed according to the ICRU Report 91 guidelines. (ICRU 2017)

4.4.8. Radiotherapy plan quality assurance review

All radiotherapy treatment plans are to be submitted electronically using the eCRF system in the DICOM-RT format to enable analysis of radiotherapy treatment plan quality including planning CT and MRI, DICOM structures and dose distribution. Analysis of radiotherapy treatment quality will be conducted by random sampling and institutions will receive feedback based on the conducted analyses. A systematic analysis of radiotherapy treatment quality will be performed after completion of accrual. Upload of the radiotherapy treatment plan must be completed within 4 weeks of treatment delivery.

4.4.9. Normal tissue constraints

The dose limits that must not be exceeded for organs at risk are listed in the table below.

Organs at Risk	Maximum Dose	
	SRS (control arm)	FSRT (investigational arm)
Optic nerves	8,0 Gy	32 Gy
Chiasma	8,0 Gy	32 Gy
Eyes (retina)	8,0 Gy	32 Gy
Brainstem	12,0 Gy	36 Gy
Pituitary gland	15,0 Gy	36 Gy
Cochlea	3,7 Gy (Mean Dose)	32 Gy
Brain tissue	See Section 4.4.10. below	

Reduction of margin:

If the planned isotropic expansion leads to overlapping with a critical organ at risk (OAR), such as the optic system, it is permissible to reduce the safety margin to 0 mm at the affected sites in both the SRS and FSRT arm.

4.4.10. Sparing of healthy brain tissue

As a basic principle, healthy brain tissue should be treated as sparingly as possible without compromising the radiation dose prescribed to the tumor.

Control arm (SRS):

$V_{10\text{Gy}}$ and $V_{12\text{Gy}}$ are well-described predictors for the occurrence of radionecrosis associated with the use of single-fraction SRS according to RTOG 9005 for brain metastases (Blonigen et al. 2010):

	SRS
	(control arm)
Normal brain	$V_{10\text{Gy}} \leq 10.5 \text{ cm}^3$ $V_{12\text{Gy}} \leq 7.9 \text{ cm}^3$

A $V_{10\text{Gy}} \leq 10.5 \text{ cm}^3$ and a $V_{12\text{Gy}} \leq 7.9 \text{ cm}^3$ are reference values in the trial, however, frequently can't be achieved with large metastases (Kirkpatrick et al. 2015, Minniti et al. 2016). Instead $V_{10\text{Gy}}$ and $V_{12\text{Gy}}$ should be minimized as far as reasonably possible as judged by the treating physician.

The following options are available in the trial, if V_{10} and V_{12} need to be further reduced at the discretion of the treating physician and other aspects of treatment planning have already been fully optimized:

- The required lower boundary for the Conformity Index is decreased to 0.9. The lower boundary for an acceptable variation for Conformity Index is reduced to 0.8.
In addition, regarding Coverage the lower boundary for per protocol is decreased to 0.8 and the lower boundary for acceptable variation is lowered to 0.7.
- It is permitted to reduce the prescription dose down to 23 - 18 Gy (diameter: $\geq 1 \text{ cm}$ and $< 2 \text{ cm}$), 17 - 15 Gy (diameter: $\geq 2 \text{ cm}$ and $< 3 \text{ cm}$) or 14 - 12 Gy (diameter: $\geq 3 \text{ cm}$ and $\leq 4 \text{ cm}$) which constituted the previous dose steps for metastases treated in the RTOG 9005 trial.
- Contact the Study coordination office ([contact])

Investigational arm (FSRT):

Maximal sparing of healthy brain tissue is also pursued in the experimental arm. The dose prescription specified in the study protocol should not be compromised, however.

4.5. Side effects of radiotherapy

Any of the general side effects of radiotherapy in the neurocranial area may, in principle, occur (see, for example, proCompliance, Documented Patient Information, Radiosurgery and Stereotactic Radiosurgery):

Common:	Edema (swelling from the accumulation of fluid in the brain), which can trigger or aggravate disease-related complaints such as paralysis, seizures and headaches Localized brain tissue death (brain necrosis), which in rare cases may be associated with neurological deficits (e.g., paralysis) Damage to healthy nerve cells cannot be ruled out with certainty and may result in temporary or, in rare cases, permanent paralysis (e.g., of the extremities or facial nerves) or loss of senses (e.g. deterioration or loss of vision, hearing loss)
Rare:	Hair loss in the irradiated area Hemorrhage in irradiated metastases
Very rare:	Wound healing disorders in the irradiated area after later surgery or injury Impairment of concentration and memory Dryness, slight redness and inflammation of the skin very rarely occur after stereotactic radiosurgery

Possible late complications of radiotherapy:

Common:	Localized brain tissue death (brain necrosis) with swelling of the surrounding tissues, which in rare cases may be associated with neurological deficits (e.g., paralysis)
Rare:	Permanent hair loss at the irradiated site Sensitivity to weather in association with headaches Rapid fatigue with increased need for sleep, reduction of mental speed; permanent reduction of concentration and memory Reduced hormone production in the diencephalon and pituitary gland (hypophysis); the resulting hormone deficits affect the metabolism and sexuality but can be compensated by hormone replacement therapy
Very rare:	Deterioration of hearing or vision Optic nerve damage, which may result in blindness Radiotherapy slightly increases the natural risk of developing a second tumor in later years. This is particularly true when combined with cytostatic chemotherapy.

4.6. Modification of the radiotherapy regimen

In principle, the study protocol does not provide for the interruption or even discontinuation of the specified radiotherapy regimen. This is only possible at the discretion of the responsible radio-oncologist if there is good reason for doing so. Likewise, the individual reference dose, total reference dose and PTV can be modified in such an event at the discretion of the radio-oncologist. The radio-oncologist must make such a decision on an individual patient basis and inform the study center of the decision. (see also the

sections: 4.4.3. Target volume delineation, 4.4.9. Normal Tissue Constraints as well as 4.4.10. Sparing of healthy brain tissue)

4.7. Systemic treatment during and in close temporal relationship to radiotherapy

Certain systemic treatments may increase the risk for side effects when administered concurrently with stereotactic radiotherapy for cerebral metastases. The following guidelines have been defined in this trial to assure a safe and standardized practice regarding systemic treatment during radiotherapy.

In addition to concurrent treatment, some high-risk systemic agents, such as BRAF-inhibitors, may also increase the risk for CNS side effects, when they are administered in close temporal relationship to stereotactic radiotherapy (see Section 4.7.1. "Additional safeguards with respect to high-risk systemic agents" below).

Control arm (SRS):

Concurrent systemic treatment should not be administered on the days, on which single-session radiosurgery (SRS) is given.

Please also notice the additional safeguards for high-risk systemic agents described below.

Investigational arm (FSRT):

Due to the prolonged treatment delivery in fractionated stereotactic radiotherapy (FSRT) certain systemic agents may be administered during radiotherapy. Table 3 and 4 provide a list of systemic treatments that may be administered during FSRT and those that must not be given during treatment.

Please also notice the additional safeguards for high-risk systemic agents described below.

**Table 3: Systemic agents that may be administered during FSRT**

Systemic agent	Source
Anti-PD-1 / Anti-PD-L1 antibodies may be given during FSRT	(Chen et al. 2018)
Bevacizumab may be given during FSRT	(Levy et al. 2014)
Capecitabine, 5-Fluorouracil may be given during FSRT	(Chargari et al. 2009)
Cetuximab may be given during FSRT	No reports of increased toxicity were identified
Cisplatin, Carboplatin may be given during FSRT	(Verduin et al. 2017)
Crizotinib, ceritinib, alectinib may be given during FSRT	No conclusive evidence of increased toxicity was identified (Kroeze et al. 2017)
Etoposide may be given during FSRT	(Chen et al. 2012)
Gefitinib/Erlotinib may be given during FSRT	(Kroeze et al. 2017)
Ifosfamide may be given during FSRT	(Quantin et al. 1999)
Ipilimumab may be given during FSRT	(Mathew et al. 2013, Kiess et al. 2015, Chen et al. 2018)
Lapatinib may be given during FSRT	(Yomo et al. 2013)
Mitomycin may be given during FSRT	(Furuse et al. 1997)
Paclitaxel, Docetaxel may be given during FSRT	(Arrieta et al. 2011)
Pemetrexed may be given during FSRT	(Dinglin et al. 2013)
Sorafenib/Sunitinib may be given during FSRT	(Kroeze et al. 2017)
Trastuzumab may be given during FSRT	(Chargari et al. 2011)
Vindesine may be given during FSRT	(Furuse et al. 1997)
Vinorelbine may be given during FSRT	(Quantin et al. 1999)

Table 4: Systemic agents that must not be administered during FSRT

Systemic agent	Source
BRAF Inhibitors (e.g. vemurafenib, dabrafenib) must not be given during FSRT	(Anker et al. 2016)
Gemcitabine must not be given during FSRT	(Huang et al. 2007)
MEK Inhibitors (e.g. trametinib and cobimetinib) must not be given during FSRT	(Anker et al. 2016)
Trastuzumab emtansine (T-DM1) must not be given during FSRT	(Carlson et al. 2014, Mitsuya et al. 2016, Geraud et al. 2017)

For agents not yet listed above please contact the Study coordination office ([contact]).

4.7.1. Additional safeguards with respect to high-risk systemic agents

BRAF- and MEK-Inhibitors:

BRAF- as well as MEK-Inhibitors (such as dabrafenib and vemurafenib as well as trametinib and cobimetinib) must not be administered ≥ 3 days before and after radiotherapy in both treatment arms (Anker et al. 2016).

Gemcitabine:

Gemcitabine must not be administered ≥ 7 days before and after radiotherapy in both treatment arms.

Trastuzumab emtansine (T-DM1):

Due to multiple reports of increased risk for radionecrosis T-DM1 must not be administered ≥ 20 days before and after radiotherapy in both treatment arms, which corresponds to 5 times the half-life (Carlson et al. 2014, Geraud et al. 2017).

5. Clinical examinations and status assessments

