5.1. Schedule of examinations and procedures

5.1.1. Screening examinations before treatment

1. Magnetic resonance imaging (MRI) of the brain

Note: Time from MRI to start of radiotherapy has to be ≤ 14 days

2. Performance status assessment

ECOG / KPS

**3. Assessment of Adverse Events before treatment
(Medical history relevant for the study)**

NCI CTCAE v5.0

4. Assessment of Quality of Life

EORTC QLQ-C30

EORTC QLQ-BN20

5. Assessment of RPA and GPA prognostic scores

6. Documentation of glucocorticoid dose

**7. Documentation of systemic treatment including prior
systemic therapies**

8. Written informed consent

9. Pregnancy test in women of childbearing potential

Pregnancy should be ruled out by determining Serum β -HCG

10. Planning CT

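### Section 4.7.1 words its three washout rules so that, read literally, they forbid distant dosing and leave the days next to radiotherapy open; the intent is clear, but the wording should be corrected

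*Protocol*

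**What the plan says.** Section 4.7 gives the reason for the rules. "In addition to concurrent treatment, some high-risk systemic agents, such as BRAF-inhibitors, may also increase the risk for CNS side effects", and the sentence goes on to say that this applies "when they are administered in close temporal relationship to stereotactic radiotherapy". The hazard is therefore dosing close in time to radiotherapy, in addition to dosing during it.

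Section 4.7.1 then sets one rule per agent group:

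- BRAF and MEK inhibitors "must not be administered ≥ 3 days before and after radiotherapy in both treatment arms".
- "Gemcitabine must not be administered ≥ 7 days before and after radiotherapy in both treatment arms".
- "T-DM1 must not be administered ≥ 20 days before and after radiotherapy in both treatment arms, which corresponds to 5 times the half-life".

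Two neighbouring rules cover the treatment days themselves. For the control arm, Section 4.7 says "Concurrent systemic treatment should not be administered on the days, on which single-session radiosurgery (SRS) is given". For the experimental arm, Table 4 lists the agents barred during the course, for example "Trastuzumab emtansine (T-DM1) must not be given during FSRT".

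**The concern.** A rule meant to keep a drug away from radiotherapy should forbid the days within N days of it. Attached directly to a prohibition, the greater-than-or-equal sign forbids the days at or beyond N instead. Someone applying the sentence exactly as it stands would get the wrong dosing window for all three agent groups.

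The rules are mandatory and apply in both arms. The T-DM1 rule is there because of reports of radionecrosis, which Section 1.6.2 names as a secondary safety outcome. At stake is whether sites handle these drugs safely and uniformly around treatment. The primary analysis is not involved.

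**Working it through.** No figure in the plan depends on this wording, so the check compares texts, with a little arithmetic for T-DM1.

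**Step 1: the literal and intended readings.** N is taken from Section 4.7.1. Days are counted outward from radiotherapy on each side.

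| Agent | N | Literal: forbidden | Literal: not forbidden by 4.7.1 | Intended: drug-free interval |
|---|---|---|---|---|
| BRAF/MEK inhibitors | 3 | day 3 and beyond | days 1 to 2 | at least 3 days |
| Gemcitabine | 7 | day 7 and beyond | days 1 to 6 | at least 7 days |
| T-DM1 | 20 | day 20 and beyond | days 1 to 19 | at least 20 days |

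The literal reading leaves N-1 days open on each side: 2, 6 and 19.

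**Step 2: which reading the protocol supports.** Section 4.7 places the risk in the days near radiotherapy. The literal reading leaves exactly those days open, so it contradicts the stated purpose.

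**Step 3: the T-DM1 rationale.** The protocol equates 20 days with five half-lives, which implies a half-life of 20 / 5 = 4 days. This value is inferred; the protocol does not state it. Assuming simple exponential elimination, the fraction remaining t days after a dose is 0.5^(t/4):

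- Dose 1 day before (not forbidden literally): 0.5^(1/4) = 0.84, about 84% remaining.
- Dose 20 days before (forbidden literally): 0.5^(20/4) = 0.5^5 = 0.03, about 3% remaining.

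Five half-lives make sense only as a minimum washout. These percentages show the direction of the rule; they do not measure risk to patients.

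**Step 4: whether another rule covers the adjacent days.** Table 4 covers dosing during FSRT. The control-arm rule in Section 4.7 covers the day of SRS. Neither reaches the days before or after, and no other section states the interval in the correct direction.

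**Step 5: whether this is a text-conversion fault.** That is unlikely. The same sign appears in all three rules, and the opposite sign comes through correctly elsewhere, for example in Section 5.1.1: "Time from MRI to start of radiotherapy has to be ≤ 14 days".

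**The case against.** The strongest reply is that only one small word is missing. If *for* is inserted before the sign, each sentence states a drug-free period of at least N days, and the direction is right. The literal reading is also one that no site could sensibly follow: it would bar these drugs at every time beyond N days and tolerate them right beside treatment, in a section headed as a safeguard. The purpose appears just before, in Section 4.7, and the half-life remark points the same way. All of this stands, and it is why the point is minor. It does not make the sentences correct: a mandatory safety rule should not depend on the reader supplying a word that sets its direction.

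Several stronger readings are tempting but unsupported:

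- *Patients have been, or will be, dosed too close to radiotherapy.* The protocol does not say how many patients receive these agents, and nothing shows a site following the literal text.
- *The radionecrosis comparison is compromised.* No effect on any endpoint can be derived from the document.
- *The values of N are wrong.* They rest on cited sources that are not at hand, and nothing in the protocol contradicts them.
- *The rule also fails because it does not settle day N itself or the reference fraction.* These are matters of detail. On the intended reading, an interval of N days suffices. Since dosing during FSRT is dealt with separately, before and after naturally refer to the start and end of the course.

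**Conclusion.** The point holds as a minor drafting defect. Three operative sentences in one section, with N = 3, 7 and 20, say the reverse of what is meant when read literally, and no other text in the protocol states the interval correctly. Because the intent can be inferred from Section 4.7 and the half-life rationale, the practical risk is small.

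The conclusion rests on the wording and its context. It needs no assumption about the number of exposed patients or about pharmacology; the 4-day half-life serves only as illustration. Sample size, event count, significance level, power and the primary analysis are unaffected.

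**What to change.** Replace the construction in each of the three rules with: *must be withheld for at least N days before the first and for at least N days after the last radiotherapy fraction*, with N = 3 for BRAF/MEK inhibitors, 7 for gemcitabine and 20 for T-DM1. In the SRS arm the first and last fraction are the same, so one sentence serves both arms. Notify the sites of the clarified text.

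The cost is three reworded sentences and a site notice. Systemic treatment is already documented at screening and at every later visit, so no new data collection is needed. The values of N and all statistical figures stay as they are.
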